10.5 Data Security and Subject Confidentiality

All evaluation forms, and reports will be identified only by a coded number to maintain patient confidentiality. All records will be kept in a locked/password protected computer. All computer entry and networking programs will be done with coded numbers only. Clinical information will not be released without the written permission of the patient, except as necessary for monitoring by the Federal funding institution (NHLBI), the DCC, or other governmental regulatory bodies.

The data coordinating center (DCC) at the University of Utah has a dedicated, locked server room within its offices, and the building has 24 hour on-site security guards. The DCC has a state-of-the-art computer infrastructure and coordinates its network infrastructure and security with the Health Sciences Campus (HSC) information systems at the University of Utah. This provides the DCC with effective firewall hardware, automatic network intrusion detection, and the expertise of dedicated security experts working at the University. Network equipment includes three high-speed switches and two hubs. User authentication is centralized with two Windows 2003 domain servers. Communication over public networks is encrypted with virtual point-to-point sessions using secure socket layer (SSL) or virtual private network (VPN) technologies, both of which provide at least 128 bit encryption. OpenClinca (OC) is the clinical trials software used at the DCC, and eRoomTM is used for communications about the study. It is possible that a different electronic data capture system could be used in the future. OC, eRoomTM and other web applications use the SSL protocol to transmit data securely over the Internet.

Direct access to DCC machines is only available while physically located inside the DCC offices, or via a VPN client. All network traffic is monitored for intrusion attempts, security scans are regularly run against our servers, and our IT staff are notified of intrusion alerts. Security is maintained with Windows 2003 user/group domain-level security. Users are required to change their passwords every 90 days, and workstations time out after 10 minutes of inactivity. All files are protected at group and user levels; database security is handled in a similar manner with group level access to databases, tables, and views in Microsoft SQL Server.

The investigators and staff of the data coordinating center are fully committed to the security and confidentiality of data collected for the THAPCA Trials. All personnel at the DCC have signed confidentiality agreements concerning all data encountered in the DCC. Violation of these agreements may result in termination from employment at the University of Utah. In addi-

tion, all personnel involved with DCC data systems have received Human Subjects Protection and HIPAA education.

10.6 Health Insurance Portability and Accountability Act

Data elements collected include the date of birth and date of admission. Prior to statistical analyses, dates will be used to calculate patient age at the time of the study events. The final data sets (used for study analyses and archived at the end of the study) will be de-identified, and will exclude these specific dates.

Data elements for race, ethnicity, and gender are also being collected. These demographic data are required for Federal reporting purposes to delineate subject accrual by race, ethnicity, and gender.

Each Clinical Center will be required to obtain informed consent from a legal guardian of eligible patients before the patient is enrolled in the study. For purposes of the DCC handling potential protected health information (PHI) and producing the de-identified research data sets that will be used for analyses, all study sites have been offered a Business Associate Agreement with the University of Utah. Copies of executed Business Associate Agreements are maintained at the DCC.

10.7 Record Retention

For federally funded studies subject to the Common Rule, records relating to the research conducted shall be retained for at least 3 years after completion of the research. Completion of the research for this protocol should be anticipated to include planned primary and secondary analyses, as well as subsequent derivative analyses. Completion of the research also entails completion of all publications relating to the research. All records shall be accessible for inspection and copying by authorized representatives of the regulatory authorities at reasonable times and in a reasonable manner [45 CFR §46.115(b)].

11 Data and Safety Monitoring Plan

11.1 Data Safety Monitoring Board (DSMB)

THAPCA will have a Data Safety Monitoring Board (DSMB) appointed by the Director of the National Heart, Lung, and Blood Institute (NHLBI). The

DSMB will have a charter, will approve the protocol prior to implementation, and will review interim analyses as described in Section 9.7 on page 63.

The purpose of the DSMB is to advise the Federal funding agency (NHLBI), the THAPCA scientific Principal Investigator ([name]), and the THAPCA Executive Committee regarding the continuing safety of study subjects and the continuing validity and scientific merit of the study. The DSMB is responsible for monitoring accrual of study subjects, adherence to the THAPCA protocol, assessments of data quality, performance of individual clinical sites, review of serious adverse events and other subject safety issues, and review of formal interim statistical analyses of treatment efficacy. The Data Coordinating Center will send reports relating to these topics to DSMB members ten days prior to each DSMB meeting. We propose that the DSMB will meet twice annually during patient accrual into the THAPCA Trials, although the DSMB will have the discretion to alter meeting timing and frequency. There are no planned DSMB meetings in the last year of the THAPCA project, during which no new patients will be enrolled (but 12 month follow-up will be conducted to obtain the primary outcome.)

The Data Coordinating Center will staff DSMB meetings. The DSMB Executive Secretary, appointed by NHLBI, will produce minutes of the meetings. The minutes will be approved by the DSMB Chairperson and sent to the Director, NHLBI, for acceptance of recommendations. The THAPCA Executive and Steering Committees will then receive the minutes.

11.2 Adverse Event Reporting

11.2.1 Definitions, Relatedness, Severity and Expectedness

Definition: An adverse event (AE) is any untoward medical occurrence experienced by a subject. An event constitutes a disease, a set of related signs or symptoms, or a single sign or symptom.

On each study day, the clinical site investigator will evaluate adverse events. Adverse events not previously documented in the study will be recorded on the adverse event record form. The nature of each experience, date and time (where appropriate) of onset, outcome, course, and relationship to treatment should be established.

Relatedness: The suspected relationship between study intervention (use of the temperature control blanket and/or hypothermia) and any adverse event will be determined by the clinical site investigator using the following criteria:

Not Related: The event is clearly related to other factors, such as the subject's clinical state, therapeutic interventions, or concomitant drugs administered to the subject.

Possibly Related: The event follows compatible temporal sequence from the time of application of the temperature blanket or changes in temperature, but could have been produced by other factors such as the subject's clinical state, therapeutic interventions, or concomitant drugs administered to the subject.

Probably Related: The event follows a reasonable temporal sequence from the time of application of the temperature blanket or changes in temperature, and cannot be reasonably explained by other factors such as the subject's clinical state, therapeutic interventions, or concomitant drugs administered to the subject.

Seriousness: The severity of clinical adverse events and laboratory abnormalities will be recorded by the clinical site investigator and categorized. A serious adverse event (SAE) is an adverse event that:

- results in death; or
- is life-threatening (the patient was, in the view of the clinical site investigator, in immediate danger of death from the event as it occurred); or
- requires inpatient hospitalization or prolongs and existing hospitalization; or
- results in persistent or significant disability or incapacity; or
- results in congenital anomaly/birth defect); or
- any other event that, based upon appropriate medical judgement, may jeopardize the subject's health and may require medical or surgical intervention to prevent one of the other outcomes listed in this definition.

Expectedness of the Event: All adverse events, including serious adverse events, will be evaluated as to whether their occurrence was expected or unexpected. An adverse event is considered expected if it is known to be associated with critical illness following cardiac arrest, the underlying medical condition of the subject, is directly related to study outcome (e.g. death), or is otherwise mentioned in the protocol, informed consent, or other study documents. For this protocol, expected events include:

- mortality (unless believed to be related to cooling)
- hemodynamic instability
- cardiac arrhythmias, including life-threatening rhythms
- electrolyte abnormalities
- metabolic acidosis
- sepsis, infections, or bacteremia
- fever
- bleeding
- seizures
- cerebral edema and other brain injury
- worsening neurological function
- renal dysfunction
- liver dysfunction
- reintubation
- hypoxia
- respiratory distress
- pleural effusions
- pulmonary edema
- anasarca (body edema)
- general pediatric problems related to ICU stay and cardiac arrest
- complications related to the condition that led to cardiac arrest

Treatment or Action Taken: For each adverse event, the clinical site will record whether an intervention was required:

- Intervention: Surgery or procedure
- Other Treatment: Medication initiation, change, or discontinuation
- None: No action taken

Finally, the clinical site will record the clinical outcome of each adverse event as follows:

- Death
- Recovered and the patient returned to baseline status
- Recovered with permanent sequelae
- Symptoms continue

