6.6.6 Family Burden

To assess the impact of the child's health status on the family, the Child's Health Questionnaire (CHQ)¹⁰¹ and the young child's version of this measure, the Infant/ Toddler Quality of Life Inventory (ITQOL)¹⁰² will be used. On both measures, scales assessing the impact of the child's health condition on parent activities and the impact of the child's health on the parent's emotional status will be employed. Additionally, in the children 5 and older, a third scale assessing limitations in family activities as a result of the child's health status will also be employed. The total score for each of these scales will be converted to a score from 0-100 to allow for comparability between the two measures. The family activities and emotional burden scales of the ITQOL and CHQ have yielded significant differences between healthy children and those with a variety of disease states^{103, 104} and between healthy children and children following traumatic injury.¹⁰⁵

7 Detailed Study Interventions

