7.3 Temperature Monitoring

Central temperature monitoring will be required during this study as alternative methods are not reliable. Core body temperature will be measured at two sites for safety, esophageal and either bladder or rectal temperature. In addition to monitoring subject temperature as described below, the water temperature of the Blanketrol III will be monitored and recorded at the same frequency as the subject central temperatures.

Esophageal probe placement will be in the distal third of the esophagus away from the airway. The appropriate sized esophageal temperature probe should be placed just prior to initiating cooling. Using the upper incisors as the marker, the following formula will be used to calculate the distance to insert the probe: $0.25 \times ht \text{ (cm)} + 4.5 \text{ (cm)} = \text{insertion distance in cm.}$ ¹⁰⁷ Proper position will be determined by chest x-ray. Repositioning will be done as needed.

NOTE: Temperature sensing foley catheters as well as temperature sensing esophageal catheters contain metal and may need to be removed prior to an MRI. Each site will need to establish MRI compatibility of temperature sensing catheters. If data are not available, the catheters will be removed at the time of MRI and replaced after leaving the MRI suite.

Temperature will be monitored continuously and recorded hourly through 72 hours and then every 4 hours thereafter through 120 hours. During the initial time to target temperature (hypothermia or normothermia) it will be recorded every 30 minutes. It will also be recorded every 30 minutes during the rewarming period for the hypothermia group. Temperature management after the initial 120 hours will be according to the usual PICU clinical practice at each site. Review of the minimum and maximum daily temperatures, including the measurement site, will be recorded through 10 days (240 hours).

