7.5.2 Analgesia

Fentanyl is the analgesic agent recommended, but not required, for use in this study. A loading dose of 2 mcg/kg will be administered for both groups at the time the interventions are initiated. Continuous infusion of fentanyl will begin at 2 mcg/kg/hr and maintained at this rate during the initial 4 hour period corresponding to time to cool in the hypothermia group. If required, up to two additional doses of fentanyl 1 mcg/kg may be given. The infusion rate can then be increased by 1 mcg/kg/hr as needed to achieve a Ramsay sedation score of 5.

If the Ramsay score is 6 (no response) after the first four hours of the intervention, the fentanyl drip will be weaned by 1 mcg/kg/hr to achieve a Ramsay score of 5. The lowest infusion dose in the initial 24 hours will be 1 mcg/kg/hr. After 24 hours, the fentanyl infusion may be weaned to off if there is no clinical shivering, patient temperature is in the appropriate target range, and the goal for sedation/analgesia is obtained (Ramsay score of 5).

Other narcotics (e.g., morphine, remifentanyl) may be used as an alternative to fentanyl at the clinical site's discretion. However, the level of analgesia should be based on the Ramsay targets outlined here.

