7.6 Use of Neuromuscular Blockade

Vecuronium is the recommended, but not required, neuromuscular blocker for the THAPCA Trials. A paralytic loading dose of 0.1-0.2 mg/kg (100-200 mcg/kg) will be administered to patients randomized to hypothermia to facilitate cooling. Repeated doses of vecuronium will be administered as needed to maintain paralysis until the patient is cooled to the therapeutic range (32-34 °C).

Once therapeutic hypothermia is achieved, neuromuscular blockade is not required, except for as needed to control shivering resistant to sedative/analgesic agents and rewarming without clinical shivering. If a cooled patient begins to rewarm above 34.5 °C in spite of the absence of clinical shivering, vecuronium in a dose of 0.1-0.2 mg/kg (100-200 mcg/kg) would be administered immediately, and continued until the patient cools to the therapeutic range (32-34 °C). Neuromuscular blockade may also be used for other aspects of care at the discretion of the primary care team (such as ventilator asynchrony).

Other non-depolarizing agents may be used during cooling and to control shivering based on the above parameters at the clinical site's discretion.

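### Relatedness in section 11.2.1 covers only the blanket and hypothermia, so harm clearly caused by protocol-directed blockade, sedation, analgesia or temperature probes is rated unrelated and misses some, not all, of the safety-reporting rules

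*Protocol*

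**What the plan says.** Section 11.2.1 asks the site investigator to judge the link between an adverse event and the "study intervention (use of the temperature control blanket and/or hypothermia". An event is *Not Related* when it is "clearly related to other factors, such as the subject's clinical state, therapeutic interventions, or concomitant drugs administered to the subject". *Possibly Related* and *Probably Related* both require a suitable time sequence "from the time of application of the temperature blanket or changes in temperature".

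The part of the protocol headed "7 Detailed Study Interventions" directs more than temperature control:

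- **Neuromuscular blockade.** Sections 7.1 and 7.6 direct paralysis during cooling; the loading dose "will be administered to patients randomized to hypothermia to facilitate cooling". Section 7.2 directs one dose in the normothermia arm under a stated fever condition.
- **Sedation and analgesia.** Sections 7.1, 7.2 and 7.5 direct both, in both arms, to a sedation-score target. Of the analgesic, section 7.5.2 says: "A loading dose of 2 mcg/kg will be administered for both groups at the time the interventions are initiated".
- **Probes.** Section 7.3 states: "Core body temperature will be measured at two sites for safety, esophageal and either bladder or rectal temperature".
- **ECMO.** Section 7.12 does not require surface cooling, sets temperature through the heat exchanger, accepts one probe or a circuit measurement, and does not require routine paralysis.

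**The concern.** The definition used to attribute harm is narrower than the package of care that randomisation brings. Followed exactly, it works the wrong way for the omitted components: the more clearly a harm comes from a protocol-directed drug or probe, the more firmly it is rated unrelated to the study.

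Two things are at stake. Several reporting rules apply only to study-related events. And counts of related events by arm could miss a harm that differs by arm, because blockade is routine in the hypothermia arm but only conditional in the other.

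**Working it through.** No arithmetic tests this point. The check sets the definition beside what section 7 directs, and then beside each reporting rule.

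**Step 1: which directed components does the definition reach?**

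| Component | Directed in | Within the 11.2.1 definition? |
|---|---|---|
| Surface blanket, either arm | 7.1, 7.2 | Yes |
| Hypothermia by any device | 7.1, 7.12 | Yes |
| Normothermia by ECMO heat exchanger | 7.12 | No; the *Possibly* and *Probably Related* wording would reach only harm that follows a temperature change |
| Neuromuscular blockade | 7.1, 7.2, 7.6 | No |
| Sedation and analgesia | 7.1, 7.2, 7.5 | No |
| Study temperature probes | 7.1, 7.2, 7.3, 7.12 | No |

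**Step 2: what rating results?** Harm clearly caused by a component in the last three rows is clearly due to a drug or a therapeutic intervention. That is the *Not Related* wording, and it has no exception for what the protocol directs. If cooling could also have contributed, the event can still be *Possibly Related*. The gap is therefore confined to clear-cut cases.

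**Step 3: which rules does a serious, unexpected event of this kind still meet?**

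| Rule | Relatedness test | Result |
|---|---|---|
| 24-hour report to the coordinating center, then expedited report to NHLBI (11.2.5) | Study-related | Missed |
| Suspension of enrolment on the medical monitor's judgment (11.2.4) | Study-related | Missed |
| Follow-up after discharge, up to 12 months from randomisation (11.2.6) | Related | Missed |
| Unanticipated problem: 24-hour report, NHLBI step and its own suspension clause (11.2.5) | Related to taking part in the trials, which is wider | Open, if the event also suggests greater risk than was known |
| 24-hour list of serious events (11.2.4) | None | Open for listed types, or if the investigator chooses to report; no expedited NHLBI step stated |
| Recording through Day 14 and DSMB review of all adverse events (11.2.5) | None | Unchanged; meetings proposed twice yearly (11.1) |

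**Step 4: what does expectedness remove in any case?** The three missed rules also require the event to be unexpected. Section 11.2.1 lists as expected hemodynamic instability, hypoxia, respiratory distress, reintubation, bleeding and infection, plus a broad entry for general problems of the ICU stay. Many plausible harms of sedation, blockade or probes are on that list and would miss the three rules under any definition of relatedness. An allergic reaction to a blocking agent, prolonged weakness or esophageal injury from a probe is not named there.

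**Step 5: how many children are exposed?** Section 5.6 plans 750 to 950 children over both trials, allocated 1:1. Sedation and analgesia are directed for all of them. The hypothermia arms would hold 750/2 = 375 to 950/2 = 475 children, which is a ceiling for routine blockade because the number on ECMO is not given. These are exposures, not events.

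**The case against.** The strongest reply is that the definition is deliberate. Section 6.2 defines the randomised treatments as hypothermia and normothermia, and says section 7 also covers monitoring and concomitant therapies. Section 7 includes ventilation, fluids, glucose and seizures too, so its heading settles nothing, and the named drugs are recommended rather than required. This stands in part: the heading alone does not make the drugs study interventions. But the protocol leaves ventilation, fluids and glucose largely to the clinical team, whereas it directs sedation in both arms and paralysis in the hypothermia arm. Only the choice of agent is optional. If these drugs count as concomitant therapies, the *Not Related* wording captures them all the more directly.

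A reader might infer that these harms leave the expedited safety rules altogether. The documents do not support that. The unanticipated-problem rule uses a wider test and has its own suspension clause, and the list in 11.2.4 has no relatedness test. Nor is blockade confined to one arm: section 7.2 directs it conditionally under normothermia, and section 7.6 allows it for other aspects of care.

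A further objection is dilution. With sedation counted as study intervention, many hemodynamic or respiratory events in ventilated children might be rated possibly related and obscure a cooling signal. That risk is real, and the fix has to deal with it.

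**Conclusion.** The point holds in limited form. A stated rule, followed exactly, rates as unrelated a harm that the protocol's own directions clearly caused. Such an event, if serious and unexpected, misses three rules and the related-event counts. Total adverse-event counts are unaffected, and the DSMB still sees every event at its scheduled meetings. The loss is in attribution and in the assured speed of reporting.

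Its size in events cannot be given, because the documents contain no rate for these harms. It is probably small, since expectedness removes many candidates and mixed-cause events stay *Possibly Related*. The conclusion assumes that investigators apply 11.2.1 as written and that the manual of operations, which is not at hand, does not widen the definition. It concerns a reporting definition only and implies nothing about which drugs, doses or probes should be used.

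**What to change.** Reconcile 11.2.1 with 11.2.4 to 11.2.6:

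- Define the study intervention, for relatedness, as the procedures and drugs the protocol directs because of randomisation: temperature control by any device, protocol-directed neuromuscular blockade, sedation and analgesia, and study temperature probes.
- Extend the *Possibly* and *Probably Related* wording to the start or use of any of these.
- Limit the *Not Related* reasons to the child's condition and to therapies the protocol does not direct.
- Record for each related event the component to which it is attributed, so that events attributed to cooling can still be tabulated separately.

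The cost is a change of definition, one added data field and a training note. Somewhat more events will be rated related, with a few more expedited reports. No dose or clinical rule changes.
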